4.5 Usability Testing

Patients will be recruited from Atrium Health Wake Forest Baptist Family Medicine – Bermuda Run, by flyer as well as community-based sampling. Patients may be eligible to participate if they are aged 45 to 75 and have a smartphone. Patients who are interested in participating will be asked to use the web app on their own smartphone. They will be asked questions about the web app's usability. Results from the interviews will be used to finalize the program. Patients will receive a \$50 gift card as a thank you. The study team will interview up to 25 patients.

5.0 Methods for Pragmatic Trial

5.1 Participant Recruitment

We will request a waiver of informed consent from the Wake Forest IRB to allow our highly pragmatic testing since the mPATH™-CRC web application delivers guideline recommended care and not experimental care.

Each week we will query the EHR to randomly select 240 potentially eligible patients who have no record of current CRC screening. We will oversample by race and ethnicity. We will then randomize these 240 patients, to receive one of four outreach messages with equal probability.

Patients will receive the invitation message as a HIPAA-compliant text message. Each invitation message includes an embedded hyperlink to the web app appended with an anonymous study identifier that allows us to track who visits mPATH™. A reminder message will be sent once weekly for two weeks (no more than 3 messages total). We will continue to send weekly outreach messages until 120 patients who are overdue for CRC screening complete the mPATH™-CRC web app.

Low socioeconomic status individuals are more likely to suffer health disparities from colorectal cancer. Therefore, it is critically important to include low income participants in colorectal cancer screening studies. To avoid coercion, participant incentives will not exceed \$50.

5.2 mPATH™-CRC Intervention

The mPATH™ homepage will inform visitors that by using the program, their deidentified data may be used in research. The mPATH™-CRC Web App takes approximately 8 to 10 minutes to complete. It begins with a brief overview of the importance of CRC screening. Then the Web App confirms patients are due for routine CRC screening and have no risk factor that would necessitate specialized screening considerations. Patients with a risk factor will be informed of their risk status and encouraged to discuss screening with their primary care provider. Patients who are confirmed due for CRC screening and are at average risk will then be shown our updated animated and narrated CRC screening decision aid video that reviews the CRC screening tests offered by each healthcare organization: colonoscopy, FIT-DNA, and FIT. Lastly, patients can request a CRC screening test directly through the mPATH™ program. mPATH™ automatically transmits test requests to the appropriate personnel (patient navigators or clinical staff) at our partnering healthcare organizations via its secure referral dashboard. These personnel then ensure requested home-based testing is delivered or colonoscopies are scheduled. Patients who request a screening test have the option to sign up for automated text message reminders to help them complete their chosen test, as we used in our prior study.³⁵

5.3 Usual Care

Patients who are not randomly selected to receive an invitation will receive usual care, which includes the organizations' standard procedures for addressing CRC screening. At AHWFB, the EHR flags patients who are overdue for CRC screening as a "care gap" that is visible to all primary care providers.

6.0 Outcomes Measures

6.1 Primary Outcome

6.1.1 Proportion of patients who are confirmed eligible for CRC screening and request a CRC screening test within the mPATH-CRC Web App.

6.2 Exploratory Outcome

6.2.1 Proportion of participants who complete the CRC screening eligibility questions within 4 weeks of the initial invitation using the mPATH-CRC Web App.

7.0 Analytic Plan

7.1 Sample Size and Power

We will consider that the cloud-based mPATH™-CRC program is feasible for increasing CRC screening uptake if at least 25% of patients who complete the app request a screening test via

the program. We chose 25% as our threshold because we acknowledge that patients may not complete screening tests they request. If only half of patients complete their requested test (which is what we observed in our prior trial), a 25% test-request rate would increase overall screening rates by 12.5%, a clinically meaningful effect for a low cost intervention.

In our ongoing study of the iPad-version of mPATH™-CRC, 38% of patients who complete the program are requesting a screening test. Conservatively assuming the actual rate of requesting a screening test in the cloud-based version is 30%, a sample size of 120 patients will result in a 90% probability of demonstrating feasibility by observing a rate of at least 25%. Therefore, messages will be sent until 120 patients have completed the app in order to evaluate feasibility. Full operating characteristics of this feasibility design for a sample size of 120 are included in table below.

Table. Feasibility operating characteristics for a sample size of 120

True Rate of Requesting a Screening Test	Probability of Demonstrating Feasibility
10%	<0.001
15%	0.003
20%	0.107
25%	0.535
30%	0.904
35%	0.993
40%	>0.999

In our ongoing trial of the iPad version of mPATH™, 50% of patients who have no record of current CRC screening in the EHR report current screening in the mPATH™ app. Based on this experience, we will conservatively estimate that 25% of patients will respond to our invitations and 50% of patients who use mPATH™ will meet our inclusion criteria of being due for CRC screening (with no risk factors) resulting in an overall weekly accrual rate of 30 patients (25% x 50% x 240). Therefore, while the sample size for our main feasibility outcome of screening decisions is 120 patients, approximately 1000 (250 per message) patients will receive an invitation for our exploratory analysis of message response rates. With a sample size of 250, the proportion who use the web app can be estimated to +/- 6.4% based on a 95% confidence interval. Based on oversampling for race/ethnicity, we anticipate that at least 50 patients from each race/ethnicity group will receive each message. With a sample size of 50, the proportion who use the web app can be estimated to +/- 14.5% based on a 95% confidence interval. The precision estimates are based on a 50% response rate as this gives the maximum half-width of a confidence interval, and therefore provides the most conservative estimate around precision.

7.2 Analysis of Primary Outcome

Feasibility will be claimed if at least 25% of patients who complete the app (regardless of randomization group) request a screening test via the program. Completion of the app is defined as using the program to a point of indicating their screening decision. This proportion will be reported along with a 95% confidence interval.

7.3 Analysis of Exploratory Outcome

Use of the web app will be defined as completing the web app's eligibility questions for CRC screening. For each of the four messages, we will calculate the proportion who use the web app

with a 95% confidence interval. We will also calculate the proportion who use the web app with a 95% confidence interval separately for each race/ethnic group for each of the four messages. We will assess for differences in response rates between messages using chi-square tests or Fisher's exact tests as appropriate. All tests will be 2-sided with a significance level of 0.05.

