3.3 Inclusion of Women and Minorities

Participants of all races and ethnicities who meet the above-described eligibility criteria are eligible to participate in this study.

Based on WFBCCC population estimates, we expect approximately 55% of participants to be women. We will oversample for non-white patients with the goal of creating a final study sample that is approximately 50% non-Hispanic white, at least 20% Black, and at least 20% Hispanic/Latinx. We anticipate 2% or less of our sample will identify as American Indian, Asian, Hawaiian/Pacific Islanders, or more than one race, reflecting the low prevalence of these races/ethnicities in the health system's older patient population. Translating this to our sample size estimate of 240, we plan to enroll at least 132 women. Similarly, we expect approximately 20% of study participants to be Hispanic/Latino (N = 48). We plan to enroll at least 20% Black or African American (N = 48), 2% or less will be American Indian, Asian, Hawaiian/Pacific Islanders, or more than one race (N = 4). Should we not meet or exceed these estimates, the PI will engage the Office of Cancer Health Equity to discuss strategies to enhance recruitment in these target populations.

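### Section 7.3 compares messages with an unadjusted test and reports message-by-race/ethnicity cells with no test of whether message effects differ by group (minor)

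*Combined protocol and SAP*

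**What the plan says.** Section 5.1 sets up the draw and the allocation: "Each week we will query the EHR to randomly select 240 potentially eligible patients", with the statement "We will oversample by race and ethnicity", followed by "We will then randomize these 240 patients, to receive one of four outreach messages with equal probability". The weekly batch is therefore the unit of both sampling and randomisation. Race/ethnicity enters the sampling only, and no stratification of the allocation by race/ethnicity is stated.

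Section 3.3 gives the intended mix as "approximately 50% non-Hispanic white, at least 20% Black, and at least 20% Hispanic/Latinx". Section 7.1 expects that "approximately 1000 (250 per message) patients will receive an invitation for our exploratory analysis of message response rates". It also expects no fewer than 50 invited per message in each race/ethnicity group, with stated precision of 6.4 points (n = 250) and 14.5 points (n = 50) for a single proportion.

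Section 7.3 reports the proportion using the web app for each message overall, and then "with a 95% confidence interval separately for each race/ethnic group for each of the four messages". The comparison between messages is: "We will assess for differences in response rates between messages using chi-square tests or Fisher's exact tests as appropriate". Tests are two-sided at 0.05. The section does not mention adjustment for week or race/ethnicity, an interaction test or a multiplicity rule. It does not say whether the tests are overall, pairwise or within group.

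**The concern.** The oversampling gives the smaller groups usable cells, and the group-by-message table is a planned output. Readers of such a table will naturally look across groups to see whether a different message did better in each. The plan has no analysis that addresses that question, and 7.1 gives precision for a single proportion but not for a difference between two messages. Chance differences in ranking could then be taken as a reason to tailor messages.

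There is also a smaller efficiency point. Week and race/ethnicity are known for every invited patient and may predict response, yet the test uses neither. Because allocation is not blocked by race/ethnicity, the cell sizes promised in 7.1 are left to chance.

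**Working it through.** **Plan's own figures.** The exact (Clopper-Pearson) 95% interval at a 50% rate runs from 43.6% to 56.4% for n = 250 (half-width 6.37) and from 35.5% to 64.5% for n = 50 (half-width 14.47). Both stated values, 6.4 and 14.5, are reproduced.

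**Inputs.** From the documents: 25% response, 240 per week, about 1000 invited (250 per message), 50 per cell in the smaller groups. Four weekly draws give 4 × 240 = 960. Assumed: the mix in 3.3 applies to those invited, so the cells per message are 0.50 × 250 = 125 for non-Hispanic white patients and 0.20 × 250 = 50 each for Black and Hispanic/Latinx patients. The true message differences and group-specific response rates are also assumed, because the documents give none.

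**1. Precision of a within-group comparison.** 1.96 × √(2 × 0.25 × 0.75 / 50) = 0.170, or about 17 points. For 80% power, a pairwise comparison needs a true difference of about 27 points at n = 50, 17 at n = 125 and 12 at n = 250.

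**2. Ranking within groups.** One message is set at 35% and the other three at 25% in every group. By simulation, the better message ranks first in 72% of runs at n = 50 and 90% at n = 125. All three groups agree on it in about 0.72 × 0.72 × 0.90 = 0.47 of runs. The simulated share with the same top message in all three groups is 46%, so they disagree in about 54%. This happens although the message effect is identical in every group.

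**3. Unadjusted versus stratified test of message** (N = 960, four weeks; stratified by group and week with a generalised Cochran-Mantel-Haenszel test; one message 10 points better).

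| Assumed group response rates | Unadjusted power | Stratified power |
|---|---|---|
| 25/25/25% | 71% | 71% |
| 35/15/15% | 71% | 74% |
| 45/10/10% | 69% | 76% |

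With no message effect, both tests reject in 4.5% to 5.1% of runs.

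**4. Cell sizes without blocking by group.** A group making up 20% of 960 has 192 members, an average of 192/4 = 48 per message. Allocating 60 per message in each weekly 240, with 48 group members per week and no regard to group, gives an expected smallest cell of about 42. Blocking within stratum would give 48/4 = 12 per message per week, so 48 in every cell.

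**5. Power of the interaction test.** Three groups and four messages give (3 − 1) × (4 − 1) = 6 df. With cells of 125/50/50, a 25% base rate and a different message favoured in each of the two smaller groups, power is 22% for a 10-point advantage, 73% for 20 and 98% for 30.

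**6. Groups outside the main three.** Section 3.3 states: "We anticipate 2% or less of our sample will identify as American Indian, Asian, Hawaiian/Pacific Islanders, or more than one race". At 2%, that is 0.02 × 250 = 5 per message, so the minimum of 50 in 7.1 can apply only to the main groups.

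**The case against.** The strongest defence is that this is an exploratory aim in a feasibility study whose primary analysis ignores message group. The imprecision at n = 50 is disclosed, and cell proportions with intervals are ordinary descriptive output that also show reach in each group. The interaction test offered as a remedy would usually be inconclusive. All of this stands, and it sets the severity.

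Four stronger readings are tempting, but the documents do not support them.

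- *The unadjusted test is biased, or contradicts the randomisation.* Allocation is equal in every weekly batch, so neither week nor race/ethnicity confounds the comparison, and the test keeps its size. Race/ethnicity is a sampling factor, so the argument for analysing as randomised applies to week only.
- *The team will choose a best message for each group.* No selection rule, overall or by group, appears anywhere. The risk lies in how the table may be read.
- *With four identical messages the groups disagree on the top one 94% of the time, so the cells are too small.* Three groups agree by chance with probability (1/4)² = 1/16, so disagreement is about 94% at any cell size. The figure says nothing about cells of 50.
- *About half of such trials would show a false within-group difference.* The 49% needs all six pairwise tests in each of three groups. Section 7.3 states neither pairwise nor within-group testing. One overall test per group would give 1 − 0.95³ = 14%.

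Nor are the cells uninformative at every effect size. At n = 50, a message that is truly 20 points better ranks first in 96% of runs.

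**Conclusion.** The point holds as a minor one. The message test in 7.3 is valid but leaves known sampling and batch information unused, at a cost of 0 to 7 power points depending on how far response differs by group. The group-by-message cells cannot reliably separate messages within the smaller groups unless true differences are about 20 points or more, and no planned analysis asks whether message effects differ by group. The 17-point half-width follows from the plan's own 25% and 50. The 54% rests on an assumed 10-point effect common to all groups and on cells of 50/50/125. The smallest-cell figure of 42 rests on a 20% share of 960 and would rise with heavier oversampling. The primary feasibility claim is unaffected.

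**What to change.** **Section 5.1.** Within each weekly draw, block the allocation to the four messages within each race/ethnicity sampling stratum.

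**Section 7.3.**

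- Name the groups to be analysed: non-Hispanic white, Black and Hispanic/Latinx.
- Specify one overall 3-df test of message, stratified by or adjusted for race/ethnicity and week (Cochran-Mantel-Haenszel or logistic model).
- Add one message-by-race/ethnicity interaction test across the named groups.
- Keep the cell proportions and intervals, state that they are descriptive, and draw no group-specific conclusion unless the interaction test supports it.

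**Section 7.1.** Limit the expected minimum of 50 per message to the named groups.

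**Cost.** A change to the randomisation list and a few sentences of analysis text, with no added patients or data. The drawback is the interaction test's low power (22% at 10 points, 73% at 20). A non-significant result would leave the group-specific question open and should not be reported as evidence that the messages work alike in all groups.

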7.4 Estimated Accrual Rate

Based on our ongoing trial experience, we will conservatively estimate that 25% of patients will respond to our invitations and 50% of patients who use mPATH will meet our inclusion criteria of being due for CRC screening without any risk factors resulting in an overall weekly accrual rate of 30 patients (25% x 50% x 240). We plan to closely monitor the accrual rate and will discontinue sending messages once 120 patients have used the app.

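### Section 7.4 stops messaging at 120 patients who have used the app, which conflicts with the 120 completers required in 5.1 and 7.1 and is wrong as written

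*Combined protocol and SAP*

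**What the plan says.** Three places in the combined protocol and SAP state when messaging ends.

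- Section 5.1: "We will continue to send weekly outreach messages until 120 patients who are overdue for CRC screening complete the mPATH™-CRC web app".
- Section 7.1: "messages will be sent until 120 patients have completed the app in order to evaluate feasibility". The same section adds that "the sample size for our main feasibility outcome of screening decisions is 120 patients".
- Section 7.4: the team "will discontinue sending messages once 120 patients have used the app".

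Two definitions bear on these words. For the primary outcome, 7.2 states: "Completion of the app is defined as using the program to a point of indicating their screening decision". For the exploratory outcome, 7.3 states: "Use of the web app will be defined as completing the web app's eligibility questions for CRC screening". In 7.4, the sentence just before the stopping rule estimates that "50% of patients who use mPATH will meet our inclusion criteria of being due for CRC screening without any risk factors".

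**The concern.** Finishing the eligibility questions and reaching a screening decision are different events. According to the description of the intervention in 5.2, a patient who answers the eligibility questions may turn out not to be due, or to have a risk factor, and is then not taken on to the decision aid. Section 7.4 itself puts the share of users who remain eligible at 50%. A count of users therefore reaches 120 well before a count of completers does.

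The count that ends messaging fixes the size of the primary sample. The stated 90% probability of demonstrating feasibility, and every row of the table in 7.1, apply to 120 completers. Stopping at 120 users would leave the primary analysis short of that number. It would also send fewer invitations, so the message response rates would be less precise than 7.1 says.

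**Working it through.** **Inputs.** From 5.1: 240 invitations per weekly batch, four messages with equal allocation, and one invitation plus weekly reminders for two weeks. From 7.1 and 7.4: 25% respond, and 50% of users are due without risk factors. From 7.1 and 7.2: 120 completers, with feasibility claimed at an observed request rate of at least 25%.

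**Step 1: the plan's own figures.** The cut-off is 0.25 × 120 = 30 requests. The exact binomial P(X ≥ 30 | n = 120, p) is 0.003, 0.107, 0.535, 0.904 and 0.993 at p = 15%, 20%, 25%, 30% and 35%, which matches the table in 7.1. The stated ±6.4% for 250 patients is the Clopper-Pearson half-width at 50% (6.37 points).

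**Step 2: which rule the accrual arithmetic supports.** Eligible users per batch: 240 × 25% × 50% = 30. Batches needed for 120: 120 / 30 = 4. Invitations: 4 × 240 = 960, or 240 per message. Section 7.1 gives this as "approximately 1000 (250 per message) patients will receive an invitation for our exploratory analysis of message response rates". Counting all users instead gives 240 × 25% = 60 per batch, 2 batches and 480 invitations, which does not fit. The arithmetic thus rules out the all-users reading. It does not by itself establish the completer rule, because it counts eligible users and allows for no drop-off before the decision. The table supplies that part, since it needs 120 completers.

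**Step 3: section 7.4 applied literally, no response delay.** Two batches reach 120 users, with 480 invitations or 120 per message. Eligible patients: 120 × 50% = 60 (95% binomial range 49 to 71). The cut-off is 0.25 × 60 = 15.

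**Step 4: section 7.4 applied literally, responses spread out.** As an illustration, assume that the 60 users from each batch respond evenly over the three message weeks, 20 per week. The cumulative count of users is 20 after week 1, 20 + 40 = 60 after week 2, and 60 + 60 = 120 after week 3. Messaging to new patients stops after three batches: 720 invitations, 180 per message. If reminders to those already invited continue, 3 × 60 = 180 users and 180 × 50% = 90 eligible patients result. The cut-off is 0.25 × 90 = 22.5, rounded up to 23. If reminders stop as well, the eligible number falls between 60 and 90.

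**Results.**

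| | Plan (120 completers) | 7.4 literal, no delay | 7.4 literal, spread over 3 weeks |
|---|---|---|---|
| Eligible for primary analysis | 120 | about 60 | up to about 90 |
| Invitations (per message) | 960 (240; plan rounds to 250) | 480 (120) | 720 (180) |
| P(claim feasibility), true 30% | 0.904 | 0.838 | 0.850 |
| P(claim feasibility), true 20% | 0.107 | 0.207 | 0.120 |
| Half-width per message at 50% | 6.4 points (n = 250) | 9.3 points | 7.5 points |

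The literal columns treat every eligible user as a completer. Patients who stop before the decision step would lower 60 and 90 further. The documents give no such rate for this app.

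**The case against.** The best defence is that the intention is plain and the verb is used loosely. Section 7.2 describes completion itself as using the program to the decision point. The hypothesis at the end of section 1.0 speaks of overdue patients who use the app when it means the primary denominator. The definition of use in 7.3 belongs to the exploratory outcome, and nothing extends it to 7.4. The operational rule is explicit in the recruitment section, and the 120 in 7.4 follows directly on an accrual rate that already counts only eligible patients.

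Much of this stands: it shows that 5.1 and 7.1 state the rule the authors meant. It does not make 7.4 correct. In section 1.0 the word is qualified by overdue status; in the stopping sentence of 7.4 it carries no qualifier. The sentence just before it applies the same verb to a group of whom only half are eligible. Read within its own section, 7.4 gives a different rule.

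A reader might go further and infer that the trial will end with about 60 patients and half its invitations. The documents do not support that. It would need staff to follow 7.4 over two explicit statements, and every response to arrive before the next batch. Reminders run for two weeks after the invitation and 6.2 allows four weeks for a response, so zero delay is an extreme case and not a central estimate.

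**Conclusion.** The stopping rule in 7.4 contradicts 5.1 and 7.1 and is wrong as written. The evident intention is 120 patients who are due for screening and complete the app, so the stated sample size and operating characteristics stand once the sentence is corrected.

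The consequence is conditional on 7.4 being applied literally. The eligible number would then fall short of 120, at about 60 to 90 depending on response timing, which the documents do not give. These counts rest on the plan's own 25% and 50% and on no drop-off before the decision. At the 38% request rate seen with the iPad version, even 60 patients would give 0.988 against 0.999 with 120, so little would be lost there. Severity is minor. Confidence is high for the contradiction and lower for any single figure for its effect.

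**What to change.** Reword the last sentence of 7.4 to say that messages stop once 120 patients confirmed due for CRC screening and without risk factors have completed the app as defined in 7.2. Keep *used* for the event defined in 7.3.

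The cost is one sentence; design and analysis do not change. Late responses from patients already invited may take the final count above 120. The size of that excess cannot be stated without response timing.
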